- AEs will be assigned a relationship (causality) to the study treatment. The Investigator will be responsible for determining the relationship between an AE and the study treatment. The type of event, organ system affected, and timing of onset of the event will be factors in assessing the likelihood that an AE is related to the study treatment. Relationship of AEs to study treatment will be classified as follows:
 - i. Definitely related: This category applies to those AEs that the Investigator feels are incontrovertibly related to the study treatment. An AE may be assigned an attribution of definitely related if or when it meets all of the following criteria: (1) it follows a reasonable temporal sequence from administration of the study treatment; (2) it could not be reasonably explained by the known characteristics of the participant’s clinical state, environmental or toxic factors, or other modes of therapy administered to the participant; (3) it follows a known response pattern to treatment with the study treatment.
 - ii. Probably related: This category applies to those AEs which, after careful medical consideration at the time they are evaluated, are felt with a high degree of certainty to be related to the study treatment. An AE may be considered probable if or when (must have three): (1) it follows a reasonable temporal sequence from administration of the study treatment. (2) It could not readily have been produced by participant’s clinical state, environmental or toxic factors, or other therapies administered to the participant. (3) Disappears or is decreased upon

discontinuation of the study treatment. (4) It follows a known response pattern to treatment with the study treatment.

- iii. Possibly related: This category applies to those AEs which, after careful medical consideration at the time they are evaluated, are judged unlikely but cannot be ruled out with certainty to the study treatment. An AE may be considered possible if or when (must have two): (1) it follows a reasonable temporal sequence from administration of the study treatment. (2) It could not readily have been produced by participant's clinical state, environmental or toxic factors, or other therapies administered to the participant. (3) Disappears or is decreased upon discontinuation of the study treatment. (4) It follows a known response pattern to treatment with the study treatment.

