- iv. Remotely related: In general, this category can be considered applicable to those AEs which, after careful medical consideration at the time they are evaluated, are judged likely to be unrelated to the study treatment. An AE may be considered unlikely if or when (must have two): (1) it does not follow a reasonable temporal sequence from administration of the study treatment. (2) It could not readily have been produced by participant's clinical state, environmental or toxic factors, or other therapies administered to the participant. (3) Disappears or is decreased upon discontinuation of the study treatment. (4) It does not follow a known response pattern to treatment with the study treatment.
- v. Unrelated: This category applies to those AEs which, after careful consideration at the time they are evaluated, are clearly and incontrovertibly due to extraneous causes (disease, environment, etc.) and determined with certainty to have no relationship to the study treatment.

4. Outcome Assessment

- The outcome of the event will be assessed as either: resolved, resolved with sequelae, ongoing, or death. Only one AE per participant is allowed to have an outcome assessment as "death." If there are multiple causes of death for a given participant, only the primary cause of death will have an outcome of death.

5. Serious Adverse Events

- A Serious Adverse Event (SAE) is defined as any AE that:
 - i. Results in death
 - ii. Is life threatening (the participant is at immediate risk of dying from the adverse experience)
 - iii. Requires participant hospitalization or prolongs existing hospitalization
 - iv. Results in persistent or significant disability/incapacity

- v. Is a congenital anomaly/birth defect
- vi. Medical or surgical intervention to prevent life-threatening illness or injury or permanent impairment to a body structure or a body function

6. Reporting SAEs

- o The Investigator is required to report all SAEs that occur from RAP treatment through 30 days post end of study. Once the investigator becomes aware of an SAE, he/she must report the SAE to the Sponsor, ZELTIQ Aesthetics, Inc. ***within 24 hours.***
 - o Contact Information:
 - Email: [REDACTED] and [REDACTED]
 - Phone: [REDACTED]

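### The checklist for Remotely related repeats two criteria that point toward the device without reversing them, so it does not separate cleanly from Possibly related (minor)

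*Combined protocol and SAP*

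**What the plan says.** The rules are in Reporting Adverse Events and Complications, item 3 (Causality Assessment). The investigator places each adverse event in one of five categories. The first four combine an opening judgement with a checklist.

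- **i. Definitely:** "An AE may be assigned an attribution of definitely related if or when it meets all of the following criteria". The three criteria are reasonable timing, no other reasonable explanation and a known response pattern.
- **ii. Probably:** "An AE may be considered probable if or when (must have three"), from four criteria: timing, no ready alternative cause, improvement on discontinuation, known pattern.
- **iii. Possibly:** for events that "are judged unlikely but cannot be ruled out with certainty to the study treatment". It uses the same four criteria with a count of two: "must have two): (1) it follows a reasonable temporal sequence from administration of the study treatment. (2) It could not readily have been produced" by other causes, then "3) Disappears or is decreased upon discontinuation of the study treatment. (4) It follows a known response pattern".
- **iv. Remotely:** for events that "are judged likely to be unrelated to the study treatment". The count is again two of four, but the list reads "1) it does not follow a reasonable temporal sequence from administration of the study treatment. (2) It could not readily have been produced by" other causes, then "3) Disappears or is decreased upon discontinuation of the study treatment. (4) It does not follow a known response pattern".
- **v. Unrelated:** no checklist, only a judgement that the cause is certainly extraneous.

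The section does not say which category applies when an event meets more than one list. The protocol also does not say which of the five categories count as related when an event is classed as an adverse device effect (ADE).

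**The concern.** Set beside Possibly, the Remotely list looks like a copy in which only criteria 1 and 4 were reversed. Criteria 2 and 3 still describe evidence for a device cause, yet here they count toward a finding of likely unrelated. A ready alternative cause, the most natural reason to think an event unrelated, earns no credit within list iv.

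Attribution is recorded for every adverse event. It feeds the ADE and serious ADE (SADE) counts in the Study Objectives and Endpoints table, and the synopsis primary safety endpoint, which concerns events attributable to the device or treatments. If the checklist steered a device-caused event into Remotely, those outputs could understate device effects. For scale, one participant out of 15 is 1/15 = 6.7 percentage points of an ADE proportion.

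**Working it through.** The plan gives no figure to reproduce, so the check is logical.

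**Inputs** (all from item 3). Four yes/no features:
- T = reasonable timing
- N = not readily explained otherwise
- D = disappears or decreases on discontinuation
- K = known response pattern

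This gives 2^4 = 16 patterns. They are logical patterns, not event probabilities. Assumptions: the slightly different alternative-cause wording in Definitely is the same feature N, and D can always be answered.

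**Rules, with 'must have' read as at least.** Let S = T + N + D + K.
- Definitely: T, N and K all present (2 patterns)
- Probably: S ≥ 3 (5 patterns)
- Possibly: S ≥ 2 (11 patterns)
- Remotely as written: (1−T) + N + D + (1−K) ≥ 2 (11 patterns)

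**Step 1: direction.** If N = D = 1, the Remote score is 2 + (1−T) + (1−K), which is always at least 2, so 4 of 4 patterns qualify. If N = D = 0, the score is (1−T) + (1−K), which reaches 2 only when T = K = 0, so 1 of 4 qualifies. More evidence for the device makes Remotely easier to meet.

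**Step 2: overlaps and gaps**, with patterns written (T,N,D,K).
- Definitely and Remotely: (1,1,1,1), so 1.
- Probably and Remotely: (0,1,1,1), (1,1,1,0) and (1,1,1,1), so 3.
- Possibly and Remotely, among the six patterns with exactly two features: all but (1,0,0,1), so 5.
- No list met: (1,0,0,0) and (0,0,0,1), so 2.

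**Step 3: possible corrections of list iv ('at least').**

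| List iv | Definitely overlap | Probably overlap | Possibly overlap (two-feature patterns) | No list met |
|---|---|---|---|---|
| As written | 1 | 3 | 5 of 6 | 2 |
| Reverse 2 only | 0 | 3 | 3 of 6 | 0 |
| Reverse 2 and 3 | 0 | 0 | 6 of 6 | 0 |
| Reverse 2, delete 3 | 0 | 0 | 3 of 6 | 0 |

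For the last row, Remotely becomes (1−T) + (1−N) + (1−K) ≥ 2, that is T + N + K ≤ 1. Definitely needs T + N + K = 3 and Probably implies T + N + K ≥ 2, so neither can overlap. Every pattern with S ≤ 1 satisfies T + N + K ≤ 1, so nothing is left out. The two-feature patterns that still overlap are the three with D plus one other feature.

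**Step 4: the 'exactly' reading.** As written, (1,1,1,1) still meets both Definitely and Remotely, the Probably overlap is 0, and 4 patterns meet no list. After reversing 2 and deleting 3, two patterns still meet no list: (0,0,0,0) and (0,0,1,0), each scoring 3 rather than 2. After reversing both, 5 meet none. The count wording therefore needs settling too.

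**Step 5: precedence.** If the order of listing is taken as 'highest met' ('at least' reading), the current text gives 2 Definitely, 3 Probably, 6 Possibly and 3 Remotely, with 2 unplaced (2 + 3 + 6 + 3 = 14 of 16). After reversing 2 and deleting 3 it gives 2, 3, 6 and 5, which is all 16. But if all 16 land in i to iv by checklist, an unrestricted highest-met rule leaves Unrelated with no event to receive.

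**The case against.** The strongest reply is that the checklists do not decide. Each category opens with a judgement, the lists say what an event may be considered, and the type of event, organ system and timing of onset are named as further factors. An investigator who is nearly certain of a device cause cannot also judge the event likely unrelated. That stands, and it disposes of the Definitely and Probably overlaps in practice. It does not settle Possibly against Remotely, where the two opening judgements lie close together and the checklist is the main guide.

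Second, on a highest-met reading the number of patterns in the top three categories is 2, 3 and 6 before and after correction. That is true, but no text states that order.

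Third, reversing criterion 3 would count persistence of an event as evidence against the device. That is awkward with three discrete sessions and follow-up to 52 weeks after the last. This stands, and it favours deleting the criterion.

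Fourth, an alternative cause already fails criterion 2 in lists i to iii, and a certain one is the basis for Unrelated. This also stands; the missing credit is confined to list iv.

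A reader might infer that device-caused events will be filed as unlikely, or that the safety results as a whole are unreliable. The documents support neither. Filing is left to judgement, and the Safety Analysis section reports incidence, severity and a complete listing whatever the attribution. All serious events are reported regardless of causality.

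**Conclusion.** The drafting error is real under either reading of the count: list iv mixes two criteria that point away from the device with two that point toward it. The absence of a precedence rule is a separate gap, and correcting list iv does not close it.

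The practical reach is narrow. Overall adverse event and serious adverse event incidence, severity, the listing and serious event reporting are untouched. ADE and SADE counts, and events called attributable to the device, are exposed only if the unstated cut-off for related falls between Possibly and Remotely or higher. If everything except Unrelated counts as related, moving an event between Possibly and Remotely changes nothing. If the cut-off is above Possibly, a change would need a Probably or Definitely event to be filed as Remotely, which the opening judgements work against. The size of any effect cannot be computed from the documents; with one site and up to 15 participants it is probably small. Severity: minor. The pattern counts rest on treating N as one feature across all lists and D as always answerable.

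**What to change.** (a) In category iv, reverse criterion 2 by striking 'not', so that a ready alternative cause counts toward Remotely. Delete criterion 3, keeping a count of two from the remaining three. Reversing criterion 3 instead also clears the Definitely and Probably overlaps and the gaps, but leaves 6 Possibly/Remotely overlaps rather than 3 and credits persistence against the device.

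(b) If a precedence rule is added, limit it to categories i to iv and apply it only after the category v judgement has ruled out Unrelated. For example: 'once Unrelated has been excluded, assign the highest of categories i to iv whose criteria are met'. Without that limit, Unrelated could not be assigned.

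(c) Write 'at least three' in category ii and 'at least two' in categories iii and iv.

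The cost is protocol and case report form instruction wording. Some events may move to a more related category. These edits do not supply the missing cut-off for related, which would have to be stated before the effect on ADE and SADE counts could be judged.

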 6. Monitoring logs and appointment schedules
 7. Investigators CVs, medical license information, and financial disclosure documentation

8. All sponsor representative/investigator correspondence, including telephone logs
9. Any other pertinent study documents

Protocol Deviations: Protocol deviations occur when there are variations in the approved study protocol, criteria, or procedure. An example of this would be a participant visit conducted outside the follow-up schedule. As protocol deviations may increase the risk or decrease the benefit of the intervention and/or affect the participant's rights, safety, welfare and/or integrity of the resultant data, investigators are required to record and report all incidences in a deviation log for adjudication during data analysis.

- iv. All protocol deviations must be reported to Sponsor in a timely manner of their occurrence. Evaluation of the deviation and its impact on the study protocol will be adjudicated on a case-by-case basis. Data discrepancies or questions resulting from reported protocol deviations will be managed between Sponsor and the site investigator or their designee.

Protocol Violation: A violation is any non-adherence to the protocol that may result in significant additional risk to the participant (e.g., enrollment of a participant who does not meet the study criteria). A protocol violation can also be an event of non-adherence to GCPs that may impact participant safety (e.g., failure to obtain proper consent before performing study procedures). Violations should be reported to the study sponsor and the IRB within 5 working days if they occur.

INVESTIGATIONAL DEVICE ACCOUNTABILITY AND STORAGE

The Sponsor will maintain full device accountability. The Investigator will maintain adequate records documenting all materials received and returned, and shipping information of the device. All used materials will be discarded by the Investigator after each treatment has been completed.

REGULATORY AND ETHICAL COMPLIANCE

1. The Study will comply with all instructions, regulations, and agreements in this protocol. In addition, the study will comply with all local regulations, external standards and applicable ICH and Good Clinical Practice (GCP) guidelines.

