The investigational site will provide direct access to all trial-related site's source data/documents, and reports for the purpose of monitoring and auditing by ZELTIQ Aesthetics, Inc. or designee, and inspection by local and regulatory authorities (as appropriate).

The investigational site will have established standard operating procedures (SOPs) for quality management. Data will be evaluated for compliance with the protocol and accuracy in relation to source documents. The study will be conducted in accordance with procedures identified in the protocol.

The data and any research conducted will be controlled by ZELTIQ Aesthetics, Inc.

STUDY RESULTS/ANALYSIS

Sample Size Determination: Up to fifteen (15) participants will be enrolled and treated in this study. The sample size is based on clinical and practical exploratory considerations and not a formal statistical power.

Demographics and Baseline Characteristics: Demographic and baseline characteristics will include age, sex, ethnicity, race, gender identity, height, and weight, Fitzpatrick Skin Type, and Cellulite Dimple assessment of bilateral posterior thighs and/or buttocks.

Study Analysis Populations: The Full Analysis Set (FAS) will include all participants who meet all the inclusion and none of the exclusion criteria, received assigned three treatments with the device and completed the 12-week, follow-up visits per the protocol. The FAS will be treated as the primary analysis set.

Effectiveness Parameter Analysis: Descriptive statistics will be performed on the population per protocol, all participants completing the study without major protocol deviations. Descriptive statistics (i.e., mean, standard deviation, etc.) will be provided for all continuous variables, percentages and frequencies for all categorical variables collected in this study.

Summary tables will be used to present population characteristics at Baseline. For categorical parameters, the number and percentage of participants in each category will be presented. The denominator for percentage will be based on the number of participants appropriate for the purpose of analysis. For continuous parameters, descriptive statistics will include n (number of participants), mean, standard deviation, median, and range. No imputation will be used to account for missing data. No processing for outliers will be performed. Data will be presented as reported on the CRF. [REDACTED]

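### Exclusions from the effectiveness analysis can turn on deviations judged case by case during data analysis, with no visible requirement that this be done before the photo results are known

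*Combined protocol and SAP*

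**What the plan says.** Two adjacent paragraphs of STUDY RESULTS/ANALYSIS point to different populations.

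- *Study Analysis Populations* defines the FAS as eligible participants who "received assigned three treatments with the device and completed the 12-week, follow-up visits per the protocol", and adds: "The FAS will be treated as the primary analysis set".
- *Effectiveness Parameter Analysis* then states: "Descriptive statistics will be performed on the population per protocol, all participants completing the study without major protocol deviations".

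The same section leaves the denominator of a percentage to whatever number of participants suits the analysis, and it rules out imputation.

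RECORDS MANAGEMENT, *Protocol Deviations*, gives a visit outside the follow-up schedule as its example of a deviation. Investigators must "record and report all incidences in a deviation log for adjudication during data analysis", and the evaluation of a deviation and its impact "will be adjudicated on a case-by-case basis". Deviations must also be reported to the sponsor in a timely manner. The section separates deviations from violations but does not grade deviations as major or minor.

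The primary endpoint (Study Synopsis, and Study Objectives and Endpoints) is the number of photo pairs correctly identified by at least 2 of 3 blinded reviewers. Its population is eligible participants who complete the 12-week visit. On size, the plan says "Up to fifteen (15) participants will be enrolled and treated in this study" and "The sample size is based on clinical and practical exploratory considerations and not a formal statistical power".

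**The concern.** The gap is wider than one undefined word. The plan states when deviations are judged (during data analysis) and how (case by case). One of its two candidate effectiveness populations excludes participants according to how serious a deviation is, and no other grading process is described. The only blinding visible in the documents is that of the photo reviewers. Nothing visible requires the classification to be finished before the reads are released.

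If the reads are available when deviations are classified, a participant's result can influence whether the deviation counts as major. That need not be deliberate. With no imputation, an excluded participant simply leaves the denominator. With at most 15 participants, one or two such decisions visibly move the main effectiveness result. The safety analysis is not affected, because its set includes everyone in whom treatment was started.

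**Working it through.** **1. Which set depends on what**

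| Population | Membership rule in the visible text | Where judgement enters |
|---|---|---|
| Primary endpoint population | Eligible, 12-week visit completed | Little |
| FAS (named primary) | Eligible, three treatments, 12-week visits as the protocol specifies | Whether an off-schedule visit still qualifies |
| Per-protocol (used for effectiveness) | Completed the study, no major deviation | What is major, and whether completion means the 12-week or the 52-week visit |

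No visible sentence says which set supplies the primary effectiveness rate.

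**2. Whether timing deviations are likely**

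The visit text puts visit 4 twelve weeks after treatment 2, which is week 4 + 12 = 16 from treatment 1. Visit 5 is at week 16 + 12 = 28. Table 1 shows weeks 12 and 24. With ±14 days, and earlier visits at their nominal dates:

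- Visit 4: weeks 14 to 18 by the text and 10 to 14 by the table.
- Visit 5: weeks 26 to 30 by the text and 22 to 26 by the table.

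Each pair of windows meets only at one edge (week 14, week 26). A visit that is on time by one source can be a deviation by the other, and visit 5 is the visit that supplies the primary photographs. These passages must be reconciled; nothing here says which is right.

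**3. Size of the effect**

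The plan gives no effectiveness figure of its own to reproduce. Assumptions, not from the documents: all 15 participants are evaluable, each contributes one photo pair, and each excluded participant is a miss with a logged deviation. With x correct identifications and d exclusions, the rate moves from x/15 to x/(15 − d).

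| Correct | d = 0 | d = 1 | d = 2 |
|---|---|---|---|
| 14 | 14/15 = 93.3% | 14/14 = 100% | not applicable |
| 12 | 12/15 = 80.0% | 12/14 = 85.7% | 12/13 = 92.3% |

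Counting areas gives the same percentages if both areas of an excluded participant were misses: 24/30 = 80.0% becomes 24/26 = 92.3%. An exclusion made without regard to outcome can go the other way: dropping one correct identification from 12/15 gives 11/14 = 78.6%.

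**4. How plausible these cases are**

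The only identification rate in the documents is 96.4%, from the single-session pivotal study described in the Introduction. If it applied here, the miss probability would be 0.036:

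- Expected misses = 15 × 0.036 = 0.54
- P(0 misses) = 0.964^15 = 0.577
- P(1) = 15 × 0.036 × 0.964^14 = 0.323
- P(2) = 105 × 0.036² × 0.964^13 = 0.084
- P(3 or more) = 1 − 0.577 − 0.323 − 0.084 = about 0.015

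So 12/15 or worse would be rare (about 1.5%), while exactly one miss would occur about a third of the time. The pivotal rate may not carry over. The chance of at least one miss, 1 − p^15, is 0.423 at p = 0.964, 0.794 at an assumed 0.90 and 0.965 at an assumed 0.80.

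**The case against.** The strongest reply is that the FAS is named primary and neither its definition nor the endpoint's population mentions major deviations. A reader might infer that membership of the primary set turns on that word; the documents do not say so. This part of the objection stands. It does not close the matter, because the next paragraph assigns the effectiveness analysis to the per-protocol population, and the FAS has its own adherence condition on the 12-week visits.

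Three further inferences are tempting but unsupported.

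- *The sponsor and investigator adjudicate deviations.* The text gives them only the data discrepancies or questions that arise from deviations. It names no adjudicator and does not itself link adjudication to analysis sets. That link is an inference from the per-protocol definition.
- *Those deciding can see each participant's result.* Open treatment does not reveal a blinded 2-of-3 read, and no visible text says when the reads reach the sponsor or the site. The documents are silent on this; they do not state that access exists.
- *Any miss could be removed.* Deviations must be logged and reported in a timely manner and the sponsor monitors adherence, so an exclusion would need a deviation on record.

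It is also fair to say that the study is exploratory and descriptive and that 12/15 is an unfavourable scenario given the pivotal rate. Redactions follow the endpoint text and the analysis paragraph, and either could hold a relevant rule.

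**Conclusion.** The concern holds in limited form. The visible plan names one set as primary, analyses effectiveness on another, and places case-by-case judgement of deviations in the analysis phase. No visible requirement makes that judgement precede the IPR results or be blind to them. Exclusion of participants with a logged deviation, decided with photo results known, is therefore permitted. The documents do not show that it is intended.

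Under the stated assumptions, the hypothetical worst case is a shift from 80.0% to 92.3% (12.3 points), and the milder case is from 93.3% to 100% (6.7 points). A reader might go on to infer an inflated false-positive rate. The documents do not support that, because the visible text plans no test, confidence interval or success threshold. What is at stake is bias in a reported percentage. If redacted text already fixes the sets before the reads are released, pointing to it would settle the timing.

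**What to change.** 1. In STUDY RESULTS/ANALYSIS, state that the FAS governs the primary effectiveness rate and that the per-protocol set is supportive. Say what completing the study means for the per-protocol set, and what adherence the FAS requires of the 12-week visit, once the visit text and Table 1 have been reconciled.
2. In *Protocol Deviations*, replace adjudication during data analysis with this rule: all deviations are classified against a prespecified list of major deviations, and the analysis sets are signed off, before IPR results are released to the sponsor or investigator.
3. Report the identification rate in all treated participants with a 12-week post-final-treatment photograph beside the per-protocol rate, and list each exclusion with its reason.

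The cost is one list and one sign-off. No extra participants, visits or procedures are needed. The reported rate may be slightly less favourable.
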